5.4. Protocol Deviations

Protocol deviations will be tabulated by treatment group (as relevant) according to categories of deviations and described in data listings, including any action taken in response to the deviation.

6. EFFICACY ANALYSIS

N/A. Efficacy will not be evaluated in this study.

7. MULTIPLE COMPARISONS AND MULTIPLICITY

No adjustments will be made for planned or unplanned multiple comparisons of study endpoints.

8. SAFETY ANALYSIS

8.1. General

An adverse event with onset during or after injection of study drug, or a worsening of an existing condition during or after injection, is considered a treatment emergent adverse event (TEAE); only TEAEs will be included in the safety analysis. All safety and local tolerability endpoints will be summarized for the Safety Analysis Set.

8.2. Compliance to Study Drug

All treated subjects will by definition be 100% compliant, as they are administered a single dose of drug which can't be discontinued.

8.3. Adverse Events

A summary table of TEAEs will include numbers of events, and numbers and percentages of subjects, experiencing: any TEAEs; serious TEAEs; related TEAEs; TEAEs by severity; TEAEs leading to study discontinuation; and TEAEs leading to death. Treatment-group differences in the percentages of subjects experiencing each TEAE category will be explored using descriptive Fisher's Exact tests. The summary table will be repeated when restricted to TEAEs with onset on or before week 52 (the end of routine follow-up).

TEAEs will be further grouped by System Organ Class (SOC) and preferred term using MedDRA™ (v23.0 or higher). Results will be displayed in order of decreasing frequency, both across SOCs and within each SOC term, by treatment group. TEAEs will also be tabulated by severity (mild, moderate, severe) and relationship to study drug, by SOC and preferred term. TEAEs (preferred term) which occur in at least 10% of subjects will be summarized separately.

Listings of TEAEs will include verbatim event description, SOC and preferred term, duration, relatedness, seriousness, severity, outcome, whether onset was during the first 52 weeks of follow-up, and whether the subject withdrew from the study as a result of the event. Information on any deaths will be described in subject narratives included in the CSR.

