1.2.2.2. Clinical Efficacy and Safety Studies

The efficacy of TV-46046 has not been evaluated.

Safety was evaluated in Study TV46046-WH-10075. The safety data indicated that treatment with 120 mg TV-46046 was well tolerated. No death, treatment related serious adverse event (SAE), or withdrawal due to adverse event (AE) occurred in this study. Twelve (100%) of the 12 subjects reported at least one AE during the course of the study. A total of 51 AEs occurred throughout the study, the majority of which (80.4%) occurred within 7.5 months of treatment initiation. Injection site reaction (ISR) was the most frequently reported AE (9 [75.0%] subjects). The rate of ISRs associated with subcutaneous injection of TV-46046 appeared to be higher compared to historical data on the approved DMPA products. However, most of the ISRs in the study were mild, transient, and resolved without sequelae. Two subjects developed skin discoloration (hypopigmentation) at the site of injection. One subject developed hypopigmentation approximately 4 months after the injection which was still present at study exit approximately one year after onset; the other subject developed hypopigmentation approximately 3 months after the injection which completely resolved approximately one year after onset.

Vital signs of all but one subject were within normal ranges and remained largely unchanged during the study compared to the baseline. With the exception of one subject in the undiluted TV-46046 group who was lost to follow-up on Day 201, all subjects in both groups returned to ovulation within 15 months of treatment initiation.

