9.6. Safety Analysis

Safety analyses will be performed on the safety analysis set. Safety measures and time points are provided in [Table 1](#).

Safety and local tolerability evaluation will be based on the following:

- occurrence of adverse events
- use of concomitant medication
- change in vital signs and body weight
- vaginal bleeding pattern
- change in mood
- change in liver function tests
- E2 levels
- delayed return to ovulation (>12 months after treatment initiation) where ovulation is defined as a single P ≥ 4.7 ng/mL
- occurrence of ISRs

No formal hypothesis tests of safety data are planned. All safety data will be summarized by treatment group using descriptive statistics (n, mean, SD, SE, median, minimum, and maximum for continuous variables, and frequency and percentage for categorical variables). Specifically, the number and percentage of subjects experiencing treatment-emergent adverse events will be

presented by treatment group, overall, by severity grade, and by relatedness to treatment. Adverse events will be further summarized in listings or frequency tables according to system organ class and preferred term. Serious adverse events and adverse events leading to withdrawal from the study will be listed separately. Concomitant medication use will be summarized by treatment group in frequency tables, by therapeutic class and medicine category. Change in vital signs (BP [systolic/diastolic], pulse, body temperature and respiration) and body weight from Day 0 to Day 7, Week 13, Week 26, and Week 52 will be described in shift tables. The percentage of women experiencing amenorrhea or vaginal bleeding disturbances (irregular vaginal bleeding or spotting) will likewise be summarized descriptively and compared between the test and reference groups. Mood data will be summarized over time from Day 0 using frequency tables and graphical displays. Liver function will be assessed by tabulating change in liver function tests from baseline to Day 7, Weeks 13, 26, and 52. Rates of return to ovulation by 12 months (Week 52), where ovulation is defined as a single $P \geq 4.7$ ng/mL, will be provided by treatment group. Estradiol concentrations will be summarized for each group using means, standard deviations, and graphical displays through Week 52. The ISR data will be provided by group in frequency tables (if applicable) and using subject-data listings.

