1. STUDY OBJECTIVES AND ENDPOINTS

The overall goal of this study is to select a dose of TV-46046 (medroxyprogesterone acetate [MPA] injectable suspension 300 mg/mL) that is safe, well tolerated, and has a pharmacokinetics profile consistent with contraceptive protection when injected every 6 months.

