2.2. Randomization, Allocation Concealment, and Blinding

Subjects will be randomized in a 1:1:1:1 allocation ratio to one of the 3 TV-46046 test groups or the Depo-subQ 104 reference group, using a permuted block design stratified by investigational center. The randomization sequence will be developed by an FHI 360 programmer not otherwise involved in the study using a validated SAS/STAT® program (version 9.4). Randomized subjects who discontinue early will not be replaced. Additional details (including block sizes) are maintained in a separate document.

Allocation will be concealed using opaque, sequentially numbered randomization envelopes provided to each investigational center. Trained staff will open the next available envelope, and allocate the next treatment assignment, only after a subject has completed all other baseline procedures and is determined to be eligible for treatment. Randomization envelopes will be

¹ The study protocol defines day of treatment initiation as Day 0. Noting that the day of treatment initiation is defined as Day 1 in CDISC, protocol Day X will be mapped to treatment Day X+1 when creating ADaM data.

Statistical Analysis Plan Version 5.0

Pharmacokinetics Study–Healthy Subjects

Study TV46046-WH-10159

maintained in a secure location at each center, with access limited to authorized personnel per center-specific study procedures.

The study will only be partially blinded due to differences in appearance of the investigational products. Investigational center staff preparing and administering injections will not be blinded but will be trained to shield the syringe from view of the subject. FHI 360 and sponsor study team members involved in assessment of adverse events, data analysis, and results interpretation will be blinded to treatment assignment until the first interim analysis, after which time only investigational center staff assessing safety outcomes or performing subject interviews will remain blinded. Lab personnel performing MPA testing will remain blinded throughout the study. Emergency unblinding procedures for medical reasons are described in the study Pharmacy Manual and Safety Management Plan. Any instances of unscheduled unblinding will be described in the CSR.

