2.5. Sample Size and Power Considerations

There are no hypothesis tests in this phase 1 pharmacokinetics study, and the sample size was not based on formal power calculations. Rather, 60 treated subjects (15 per group) was determined to be sufficient to inform the selection of a dose of TV-46046 for future pivotal study based on the results of two recent trials of MPA products implemented under similar protocols. [REDACTED]

[REDACTED]

[REDACTED]

Statistical Analysis Plan Version 5.0

Pharmacokinetics Study–Healthy Subjects

Study TV46046-WH-10159

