8.4. Injection Site Reactions

A summary table of ISRs will include numbers of events, and numbers and percentages of subjects, experiencing a) any ISR; b) ISRs documented as adverse events on CRF data (per protocol criteria); and c) hypopigmentation events. Exact Cochran-Armitage tests of trend will be used to explore relationships between MPA dose and the probability of experiencing ISRs.

ISRs will be further tabulated according to specific categories, including but not necessarily limited to erythema, swelling, pruritus, bleeding, bruising, hypopigmentation, atrophy, and injection site pain. The maximum recorded size of ISRs (if applicable) will be summarized using descriptive statistics for continuous variables. An 11-point numeric rating scale will be used to describe reports of injection site pain. Listings of ISRs will include time to onset, duration,

Statistical Analysis Plan Version 5.0

Pharmacokinetics Study–Healthy Subjects

Study TV46046-WH-10159

outcome, and whether the ISR was self-reported by the subject or noted by clinic staff when performing an assessment of the injection site.

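### The planned between-arm statistics for adverse events and injection site reactions are p-values only; at 15 women per arm they say little, and no difference with a confidence interval is planned beside them

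*SAP*

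**What the plan says.** SAP 1 sets the aim: "The overall goal of this study is to select a dose of TV-46046 (medroxyprogesterone acetate [MPA] injectable suspension 300 mg/mL) that is safe, well tolerated", with a pharmacokinetic profile suited to six-monthly injection. The first secondary objective (SAP 1.2.1; Protocol 2.1) is to evaluate and compare safety and local tolerability across the three doses and Depo-subQ Provera 104.

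The between-arm statistics planned for that comparison are:

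- **Treatment-emergent adverse events (TEAEs), SAP 8.3.** Event counts and the numbers and percentages of women are tabulated for any, serious, related, by severity, leading to discontinuation and leading to death. The groups are then compared: "Treatment-group differences in the percentages of subjects experiencing each TEAE category will be explored using descriptive Fisher's Exact tests". The form of the test (each dose against the reference, or one four-group test) is not stated.
- **ISRs, SAP 8.4.** The table has three rows: a) any ISR, b) ISRs recorded as adverse events, c) hypopigmentation. The comparison is: "Exact Cochran-Armitage tests of trend will be used to explore relationships between MPA dose and the probability of experiencing ISRs". Whether the 104 mg reference arm enters the trend is not stated.

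Protocol 9.6 says: "No formal hypothesis tests of safety data are planned". SAP 7 makes no multiplicity adjustment. Intervals do appear elsewhere: an exact 95% interval within each group for delayed return to ovulation (SAP 8.5) and 90% intervals for geometric mean ratios (SAP 10.6). Neither SAP 8.3 nor SAP 8.4 plans one.

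**The concern.** A p-value answers a yes/no question that this study was not sized to answer. With few women per arm, non-significant results are likely beside the serious, related and severe rows even if a dose truly causes a large excess. The reader would have the percentages and a p-value, but no statement of the range of excess harm compatible with the data.

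That range is what a dose-selection decision needs. Two arms with one event each and two arms with none both give p = 1.0, yet neither result excludes a difference of 20 points. A descriptive safety analysis, which is what Protocol 9.6 calls for, is better served by an estimate with an interval than by a test.

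**Working it through.** **Inputs from the documents.** Arm size is 15: "60 treated subjects (15 per group) was determined to be sufficient" (SAP 2.5). Allocation is equal: "Subjects will be randomized in a 1:1:1:1 allocation ratio" (SAP 2.2). The Safety Analysis Set keeps every treated woman, so 15 per arm is the right planning number even with later dropout.

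**Assumptions, because the documents give no figure.** Two-sided 5% level; pairwise form, one dose against the reference; a true excess of 30 points; reference rate p from 0% to 70%, the whole range in which a 30-point excess is possible. The plan states no power or detectable difference for safety, so there is no figure of its own to reproduce.

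**Step 1: counts needed for significance.** With no reference events, the two-sided Fisher p-value for t events in the dose arm is 2·C(15,t)/C(30,t).

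- t = 4: 2 × 1,365 / 27,405 = 0.0996
- t = 5: 2 × 3,003 / 142,506 = 0.042

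So 5 of 15 against 0 of 15 is the smallest significant result. With 1, 2 or 3 reference events, the dose arm needs 7, 9 or 10.

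**Step 2: chance of missing a true 30-point excess.** Power = Σ b(r; 15, p) · b(t; 15, p + 0.30) over all pairs (r, t) with Fisher p ≤ 0.05, where b is the binomial probability. At p = 0 the reference count is always 0, so power is P(T ≥ 5) for T ~ Bin(15, 0.30), which is 0.485, and the miss rate is 51.5%. Full enumeration gives:

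| Reference rate | Dose rate | Missed |
|---|---|---|
| 0% | 30% | 51.5% |
| 5% | 35% | 60.4% |
| 10% | 40% | 67.5% |
| 20% | 50% | 75.4% |
| 35% | 65% | 77.3% |
| 50% | 80% | 75.4% |
| 60% | 90% | 67.5% |
| 70% | 100% | 51.5% |

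The range is 52% to 77%.

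**Step 3: sensitivity to the assumptions.**

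- At a one-sided 5% level the miss rate is 30% to 64%.
- With 13, 14 or 16 per arm (two-sided 5%) it is 65% to 74%, 58% to 79%, or 45% to 73%.
- A four-group Fisher test, with only the 240 mg arm carrying the excess, has simulated power of 36% to 71%, so it misses 29% to 64%.
- An exact trend test with scores 104/120/180/240, in the same setting, has simulated power of 40% to 87%, so it misses 13% to 60%.

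**Step 4: what the tabulated percentages would show.** Under a true 30-point excess at 15 per arm, the dose arm's percentage is above the reference in about 94% to more than 99% of trials. It is at least 20 points above in 78% to 87%.

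**Step 5: what an interval adds.** The 95% Miettinen-Nurminen limits are the values Δ that solve (p̂_T − p̂_R − Δ)² / {[p̃_T(1−p̃_T)/15 + p̃_R(1−p̃_R)/15] × 30/29} = 1.96², with p̃ the estimates constrained to differ by Δ. For 0 of 15 against 0 of 15 the constrained estimates at the upper limit are Δ and 0. The equation becomes Δ/(1−Δ) = 3.84 × 30/(29 × 15) = 0.265, so Δ = 0.265/1.265 = 0.21.

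| Dose | Reference | Fisher p | Difference, 95% interval (points) |
|---|---|---|---|
| 0/15 | 0/15 | 1.0 | −21 to +21 |
| 1/15 | 1/15 | 1.0 | −25 to +25 |
| 3/15 | 1/15 | 0.60 | −14 to +41 |
| 4/15 | 0/15 | 0.10 | +3 to +52 |

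In none of these would the planned p-value show how large an excess remains possible.

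**The case against.** The strongest defence is that this is a 60-woman phase 1 pharmacokinetic study. Its plan says the sample size does not rest on power, labels the Fisher tests descriptive and sets no significance rule. Safety oversight uses count-based review triggers (Protocol 4.4), and anyone can compute an interval from the planned tables. All of this is true and limits the weight of the point. It does not remove it: an unpowered comparison is better reported by an interval than by a p-value, and the Protocol 4.4 triggers count events across all groups, so they do not compare doses.

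Four stronger readings are tempting, and the documents do not support them.

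- **A harmful dose would usually look no different from the reference.** Percentages by arm are tabulated, with severity, relatedness and listings, and Step 4 shows that a 30-point excess would nearly always be visible in direction. A non-significant descriptive p-value is not a finding of no difference.
- **The miss rate is two-thirds or more throughout.** That holds only for reference rates of about 10% to 60%. At 5% or below, which may apply to serious events, it is 52% to 60%.
- **The any-TEAE row must sit at its ceiling.** The earlier 120 mg study did report "Twelve (100%) of the 12 subjects reported at least one AE during the course of the study". But here ISRs count as adverse events only above set thresholds (Protocol 5.1.9), and irregular bleeding generally does not count (Protocol 5.2.1). The earlier rate need not carry over.
- **The tests fall short of a required power.** The plan sets no such requirement. The trend-test figures also change with whether the 104 mg MPA reference arm is included, which SAP 8.4 leaves open.

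**Conclusion.** The point holds in a limited form. For TEAE categories the only planned between-arm statistic is a Fisher p-value of unstated form, and for ISRs it is an exact trend p-value. No difference or interval accompanies either, although comparing safety is a stated objective. Under a pairwise two-sided 5% test with 15 per arm, a true 30-point excess is missed in about 52% to 77% of trials. The pairwise form, the level, the 30-point excess and the reference rates are assumptions. The four-group form misses somewhat less often when a single dose carries the excess.

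The defect lies in how the comparison is reported. It does not mean that harm would go unseen. Because the study is descriptive and unpowered by its own account, this is a cheap improvement, not a threat to the trial's conclusions.

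**What to change.** In SAP 8.3, and for ISR rows a) to c) in SAP 8.4, add text to this effect:

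> For each category, the difference in the percentage of women affected (each TV-46046 dose minus Depo-subQ Provera 104) will be presented with a 95% confidence interval suited to small samples (for example Miettinen-Nurminen or an exact unconditional interval). Absence of statistical significance will not be read as evidence that a dose is as safe or as well tolerated as the reference.

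If the Fisher and trend p-values are kept, show them only beside these intervals, and state whether the Fisher test is pairwise or four-group and whether the reference arm enters the trend. Record the change, and its timing relative to unblinding, in SAP 12.

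The cost is a few sentences and some extra table columns, with no new data and no additional women. The downside is that the intervals will be wide, often 20 to 30 points on each side, and unadjusted for multiplicity. The safety summary will look less reassuring, but that reflects what 15 women per arm can show.

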1.4. Study Design Rationale

1.4.1. General Study Design Rationale

This is a randomized, partially-blinded dose-range finding study to evaluate and compare the pharmacokinetics of MPA, safety and local tolerability, and acceptability of the single subcutaneous administration of 3 doses of TV-46046 300 mg/mL (120 mg/0.4 mL, 180 mg/0.6 mL, or 240 mg/0.8 mL), and 104 mg/0.65 mL of Depo-subQ Provera 104 in healthy female subjects of reproductive age.

Study participation will consist of a screening period (approximately 1.5 months, or 6 weeks), treatment initiation (Day 0), and at least 52 weeks of follow-up. Subjects with unresolved ISR(s) at Week 52 will be followed every 3 months through the resolution of ISR(s) or Week 78, whichever comes first. Approximately 60 eligible subjects will be enrolled into the study and randomly assigned in a 1:1:1:1 ratio to receive one of the 4 study treatments: 120 mg/0.4 mL, 180 mg/0.6 mL or 240 mg/0.8 mL of TV-46046, or 104 mg/0.65 mL of Depo-subQ Provera 104 (approximately 15 women per group). After treatment initiation, subjects will be followed for 52 weeks and provide blood samples for MPA, progesterone (P, and estradiol (E2) as shown in [Table 1](#).

In addition to frequent laboratory visits there will be four scheduled follow-up visits at Week 1 (Day 7), Week 13, Week 26, and Week 52, during which subjects will be evaluated for vital signs, body weight, liver enzymes, and ISRs. Vaginal bleeding pattern, acceptability, and mood will be assessed throughout the study at predefined time points. Urine pregnancy test will be performed periodically and information on adverse events and concomitant medicines will be collected throughout the study.

The study schematic diagram is shown in [Figure 1](#). Study procedures and assessments with scheduled time points are shown in [Table 1](#).

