^e ISRs will be evaluated on Day 0 immediately (ie, as soon as possible but no later than 10 minutes upon removing the needle) and 1 hour (\pm 5 minutes) after injection; Day 7; at Weeks 13, 26, and 52 and at other visits, if indicated. Subjects who have ISR(s) at Week 52 will be followed every 3 months (at Weeks 65 and 78) until ISR resolution or Week 78, whichever is earlier. If the subject does not have any ISRs at Week 52 it will be her final visit. All subjects will be instructed to return to the clinic if any ISRs develop after their final visit.

^f During laboratory visits, information on adverse events and concomitant medications will not be solicited, but will be documented if self-reported by the subject. Adverse events and use of concomitant medications will also be evaluated during additional ISR follow up at Weeks 65 and 78.

^g Liver function testing will be done at Screening, Day 7 and at the Weeks 13, 26, and 52.

^h Mood will be evaluated on Days 0 and 28; Weeks 8, 13, 17, 21, 26, 32, 36, 40, 44, 48, and 52.

ⁱ Vaginal bleeding pattern will be assessed at Weeks 13, 26, and 52.

^j Normal mammogram results from within the last year must be presented prior to enrollment for women 40 years of age or older.

^k Pap test will be completed for women who do not have results of their previous Pap test that are within American College of Obstetricians and Gynecologists (ACOG) Pap test standard of care requirements. If additional testing is

required based on Pap results, this should be completed prior to enrollment (in accordance with [Committee on Practice Bulletins Gynecology 2016](#)).

¹ Acceptability data will be collected at Weeks 26 and 52.

E2= Estradiol; ISR=injection site reaction; Lab = laboratory; MPA = medroxyprogesterone acetate; P= Progesterone

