3.4.3. Procedures for Follow-Up

Study follow-up will last for at least 52 weeks from treatment initiation. There will be four scheduled follow-up visits at Week 1 (Day 7), Week 13, Week 26, and Week 52, during which subjects will be evaluated for vital signs, body weight, liver enzymes, ISRs, adverse events and

use of concomitant medications. Vaginal bleeding pattern, acceptability and mood will be evaluated throughout the study at pre-defined time points (See [Table 1](#)). Urine pregnancy tests will be administered periodically starting at Week 26 through the end of the study.

In addition to the scheduled follow-up visits, subjects will return for laboratory visits to provide blood samples for MPA, P, and E2 at pre-defined time points (see [Table 1](#)).

If the subject has new or ongoing ISRs at Week 52, she will be followed every 3 months (at Weeks 65 and 78) until ISR resolution or Month 18 (Week 78), whichever is earlier. If the subject does not have any ISRs at Week 52 it will be her final visit. However, all subjects will be instructed to return to the clinic if any ISRs develop after their final visit. In that case, their status will change from completed the study to active and they will be followed per the schedule above until ISR resolution or Week 78, whichever is earlier.

Follow up visits should be scheduled using the target window periods below. However, if a subject cannot attend a visit within the target window below, the visit procedures should be conducted as soon as possible regardless of timing.

Table 2: Target Time Windows for Follow-up Visits

Target visit date	Target time window
Days 1, 2	± 1 hour
Days 3, 5, 7	± 3 hours
Days 10, 12, 14, 18	± 24 hours
Any scheduled clinic or laboratory visit past Day 21	± 48 hours

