5.2.2. Recording and Reporting Adverse Events

For adverse event recording, the study period is defined for each subject as that time period from signature of the ICF through the end of the follow-up period. For this study, the follow-up period is defined as up to 78 weeks after the last dose of IMP.

All adverse events that occur during the defined study period must be recorded on the source documentation and transcribed onto the CRF, regardless of the severity of the event or judged relationship to the IMP. For serious adverse events, a Serious and Protocol Defined Adverse Event Form must also be completed and must be reported immediately. The investigator does not need to actively monitor subjects for adverse events once their follow-up period has ended. Serious adverse events occurring in a subject after study discontinuation will be reported to the sponsor if the investigator becomes aware of them, following the procedures described in Section 5.2.5.

At the scheduled visits, the investigator will question the subject about adverse events by asking an open-ended question such as, “Have you had any unusual symptoms or medical problems since the last visit? If yes, please describe.” At all other visits information on adverse events will be recorded if self-reported by study subjects. All observed or reported signs and symptoms will be recorded individually, except when considered manifestations of a medical condition or disease state. A precise diagnosis will be recorded whenever possible. When such a diagnosis is made, all related signs, symptoms, and any test findings will be recorded collectively as a single diagnosis on the CRF and, if it is a serious or protocol defined adverse event, on the Serious Adverse Event Form.

The clinical course of each adverse event will be monitored at suitable intervals until resolved or stabilized or returned to baseline, through the subject’s final study visit.

The onset and end dates and times, action taken regarding IMP, treatment administered, and outcome for each adverse event must be recorded on the source documentation and transcribed onto the CRF.

The relationship of each adverse event to IMP and study procedures, and the severity and seriousness of each adverse event, as judged by the investigator, must be recorded as described in Section 5.2.3, Section 5.2.4, and Section 5.2.5.

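### Only the TEAE summary table gets a Week 52 version; the term-level tables can still mix 52 weeks of follow-up with up to 78 weeks in women who have long-lasting or late injection site reactions

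*SAP*

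**What the plan says.** **Who is observed, and for how long.** All women are followed to Week 52. Beyond that, Protocol 1.4.1 says: "Subjects with unresolved ISR(s) at Week 52 will be followed every 3 months through the resolution of ISR(s) or Week 78, whichever comes first". Protocol 3.4.3 says of the others: "If the subject does not have any ISRs at Week 52 it will be her final visit". A woman who comes back with an ISR after her final visit re-enters follow-up: "their status will change from completed the study to active". SAP 2.1 describes the same scheme.

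**What is collected after Week 52.** Protocol Table 1, footnote f: "Adverse events and use of concomitant medications will also be evaluated during additional ISR follow up at Weeks 65 and 78". Protocol 5.2.2 sets the outer limit of recording: "For this study, the follow-up period is defined as up to 78 weeks after the last dose of IMP".

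**What counts as treatment-emergent.** SAP 8.1: "An adverse event with onset during or after injection of study drug, or a worsening of an existing condition during or after injection". No end date is given, so events after Week 52 qualify.

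**Which tables are restricted.** SAP 8.3 describes a summary table (any, serious, related, by severity, leading to discontinuation, leading to death), then descriptive Fisher's exact tests between groups, and then: "The summary table will be repeated when restricted to TEAEs with onset on or before week 52 (the end of routine follow-up". The tables by SOC and preferred term, the same tables split by severity and by relationship, and the at-least-10% table follow with no stated Week 52 version. The listings show whether each onset fell in the first 52 weeks. SAP 5.2 plans women-years of follow-up by treatment group as part of disposition.

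**The concern.** Entry to the extra follow-up depends on an outcome of treatment. A woman whose ISR persists has up to 78/52 = 1.5 times the planned observation of a woman without one, and any unrelated illness she has in that time enters the unrestricted tables. If such ISRs are more common in one arm, that arm shows more events even when the drug causes none of the others.

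This is plausible here. Protocol 1.2.2.2 reports that ISRs with TV-46046 appeared more frequent than in historical data on approved products, and that two of 12 women had hypopigmentation lasting about a year or more. Comparing safety between arms is a secondary objective (SAP 1.2.1). The term-level tables show which events differ, and these are the tables with no stated Week 52 version.

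**Working it through.** The documents give no power or error-rate figure that bears on this point, so there is no design figure to reproduce. The steps below check the inputs and then give the scale.

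**1. Late events in the earlier study.** Protocol 1.2.2.2: "A total of 51 AEs occurred throughout the study, the majority of which (80.4%) occurred within 7.5 months of treatment initiation". 41/51 = 80.4%, which matches, and leaves 51 − 41 = 10 later events in 12 women.

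**2. Late event rate.** The study's length is not stated; assume 15 to 18 months. One hypopigmentation case began at about 4 months and was still present at exit about a year later, which puts that exit near month 16.
- Exit at 15 months: 10 / (12 × 7.5) = 0.111 events per woman-month
- Exit at 18 months: 10 / (12 × 10.5) = 0.079 events per woman-month

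Over 6 extra months (26 weeks) this is 0.67 or 0.48 events per woman.

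One of the 12 women was lost at Day 201, before month 7.5. Dividing by 11 women raises both figures by 12/11, to 0.73 and 0.52.

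**3. How many women might be extended.** The two hypopigmentation cases began at about 3 and 4 months and lasted about a year or more, so both were present at month 12 and would have met this study's Week 52 criterion. Scaling: 2/12 × 15 = 2.5 women per arm of 15.

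**4. Effect on follow-up and event counts.** Let k women in an arm of 15 go to Week 78. Women-years = (15 × 12 + 6k)/12. Extra events = k × (0.48 to 0.67).

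| k | Women-years | Relative follow-up | Extra events |
|---|---|---|---|
| 0 | 15.0 | 1.00 | 0 |
| 2 | 16.0 | 1.07 | 1.0 to 1.3 |
| 2.5 | 16.25 | 1.08 | 1.2 to 1.7 |
| 3 | 16.5 | 1.10 | 1.4 to 2.0 |

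With the 11-woman denominator, the range over k = 2 to 3 is 1.0 to 2.2.

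**5. Effect on subject percentages.** Take a category with 40% incidence by Week 52 and a constant hazard. By Week 78 it is 1 − 0.6^1.5 = 53.5%. With k = 3, the expected count is 3 × 0.535 + 12 × 0.40 = 6.4 of 15, against 6.0.

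**6. Effect on the Fisher's tests.** Exact enumeration was used for 15 against 15, two-sided 0.05, with equal hazards. At 40% incidence the rejection rate is 1.6% with no extension in either arm and 1.7% with k = 3 against 0.

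**7. After restriction to onset by Week 52.** The planned limit is 52 weeks in every arm, and the excess from later follow-up is zero.

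**The case against.** The strongest reply is that the SAP has already seen the problem. The restricted summary table gives any, serious and related events, overall severity, discontinuations and deaths at equal planned follow-up, as events and as subject percentages. Each listed event is marked by onset period, and women-years by group make unequal follow-up visible. Putting all events first also keeps late events in the main safety display. The tests are descriptive, and the interim analysis that informs dose selection is triggered when at least 80% of women could have reached 7.5 months, so few post-Week 52 events would exist by then. All of this stands and limits the importance of the point.

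Three stronger readings are tempting, and the documents do not support them.
- A reader might infer that any arm with more ISRs gets longer follow-up. Early ISRs that resolve add none, and extension ends at resolution. Protocol 1.2.2.2 says most ISRs in the earlier study were mild and transient.
- A reader might infer that severity and relatedness are never shown at equal follow-up. Overall they are, in the restricted summary table; only the splits by term are not.
- A reader might suppose a third or half of an arm goes to Week 78. Nothing in the documents supports this; the only data there are two cases in 12 women.

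The reply does not close the gap in the term-level tables. The listings let a reader rebuild those tables by hand but do not supply them, and SAP 5.2 does not make women-years a denominator for adverse events.

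**Conclusion.** The point holds as a cheap improvement to SAP 8.3. The SAP's own Week 52 restriction stops at the summary table, so the SOC/preferred-term tables, their severity and relationship splits, and the at-least-10% table can carry extra events from follow-up that depends on a treatment outcome. The text also leaves open which version the Fisher's tests use.

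The size is about 1 to 2 extra events in an arm of 15. This rests on 2 to 3 women being followed to Week 78, an assumed exit at 15 to 18 months in the earlier study, and its late event rate carrying over to months 12 to 18.
- Two long-lasting cases, all at 120 mg, are a thin base for the first assumption.
- One of the two resolved at about month 15, so extension to Week 78 for every such woman is on the high side.
- Events in the earlier study fell from about 41/7.5 = 5.5 per month to about 1.0 to 1.3 per month. If the decline continued, the late rate overstates months 12 to 18.

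Subject percentages and tests barely move. The at-least-10% table is where a single woman can matter: if that threshold is applied per arm (the SAP does not say), one more woman takes a term from 1/15 = 6.7% to 2/15 = 13.3%.

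**What to change.** In SAP 8.3:
- Apply the existing Week 52 onset restriction to the SOC/preferred-term tables, their severity and relationship splits, and the at-least-10% table, or add a Week 52 version of each.
- State that the Fisher's exact tests use the Week 52 version.
- Show treatment-emergent events with onset after Week 52 in a separate table by arm, with the number of women followed past Week 52 and their women-years after Week 52.

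**Cost.** SAP wording and one onset filter; the onset indicator is already planned for the listings. Post-Week 52 women-years are a small new calculation, because SAP 5.2 plans only totals. The downside is that late events sit in a separate table and must be cross-referenced. No late event is lost.
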